8.1.2 Categorizing COVID-19 disease severity

Categorization of PCR positive COVID-19 disease severity will be in accordance with the FDA’s document: COVID-19: Developing Drugs and Biological Products for Treatment or Prevention Guidance for Industry (May 2020). Patients with Critical Disease would meet exclusion criteria and not eligible for participation.

- **Mild** disease (meeting all inclusion and no exclusion criteria): Symptoms of mild illness that could include fever, cough, sore throat, malaise, headache, muscle pain, gastrointestinal symptoms, without shortness of breath or dyspnea and no clinical signs indicative of moderate, severe, or critical severity.
- **Moderate** disease (meeting all inclusion and no exclusion criteria): could include any symptom of mild illness or shortness of breath with exertion. Clinical signs suggestive of moderate illness, such as respiratory rate ≥ 20 breaths per minute,

saturation of oxygen (SpO₂) > 93% on room air at sea level, heart rate ≥ 90 beats per minute and no clinical signs indicative of severe or critical severity.

- **Severe** disease (meeting all inclusion and no exclusion criteria): could include any symptom of moderate illness or shortness of breath at rest, or respiratory distress. Clinical signs indicative of severe systemic illness, such as respiratory rate ≥ 30 per minute, heart rate ≥ 125 per minute, SpO₂ ≤ 93% on room air at sea level or PaO₂/FiO₂ < 300 and no criteria of critical severity.
- **Critical** disease: evidence of critical illness, defined by at least one of the following: 1) respiratory failure defined based on resource utilization requiring at least one of the following: endotracheal intubation and mechanical ventilation, oxygen delivered by high-flow nasal cannula (heated, humidified, oxygen delivered via reinforced nasal cannula at flow rates > 20 L/min with fraction of delivered oxygen ≥ 0.5), noninvasive positive pressure ventilation, ECMO, or clinical diagnosis of respiratory failure (i.e., clinical need for one of the preceding therapies, but preceding therapies not able to be administered in setting of resource limitation); 2) shock (defined by systolic blood pressure < 90 mm Hg, or diastolic blood pressure < 60 mm Hg or requiring vasopressors); or 3) multi-organ dysfunction/failure.

8.1.3 Vital sign assessment

Vital signs will be assessed and recorded each morning at approximately the same time of a given study day.

Vital signs to be assessed and recorded include: respiration rate (breaths per minute), oxygen saturation, supplemental oxygen use (yes/no), fraction of inhaled oxygen (FiO₂), sternal capillary refill time, body temperature, dehydration, blood pressure, heart rate (beats per minute and level of consciousness graded on the AVPU scale (Alert, Verbal = voice response present, Pain = pain response present, Unresponsive) (worst score on the assessment day for each).

8.1.4 Recording SoC medications, treatments & laboratory test results

Concomitant medications/therapy will be recorded daily ([Section 6.5](#)). The list of prohibited medications/therapy is provided in Section 6.5. Concomitant medications taken as part of SoC for COVID-19 infection treatment, and which may include: angiotensin converting enzyme inhibitors, angiotensin II receptor blockers, antibiotics, anti-fungal agents, anti-viral agents (e.g., remdesivir), inhaled or oral corticosteroids, immune-suppressant agents, intravenous fluids, non-steroidal anti-inflammatory agents, or oral/orogastric fluids, or other medications (as specified).

Status of supportive treatments received as part of SoC for COVID-19 infection treatment will be recorded daily (yes/no and details as applicable in the eCRF). These may include treatments such as: oxygen therapy and details, high flow oxygen use, non-invasive ventilation, invasive ventilation, prone positioning, inhaled nitric oxide, tracheostomy inserted, ECLS/ECMO, renal replacement therapy or dialysis, vasopressor/inotropic agent use, use of neuromuscular blocking agents, other interventions or procedures (specified). Any blood gas analyses and results and any new infection occurring during participation, regardless of organism (i.e. viral or non-viral), should be captured along with the site of infection and source of culture (e.g., BAL, tracheal aspirate, sputum, blood, urine etc.).

Routine laboratory and imaging tests performed as recommended by the treating physician (refer to [Appendix 3](#)) will be recorded as they are performed. Some tests may be recorded more frequently (e.g., white blood cell count, neutrophil count, lymphocyte count, creatinine values) than others (e.g., inflammatory markers and liver function tests).

8.2 Screening/baseline and Day 1

Activities related to the screening/baseline and Day 1 visits are listed in **Table 11** and **Table 12**. The Screening/baseline eCRF and the Daily eCRF must be completed pre-randomization and pre-study medication dose (if applicable).

Table 11. Screening/baseline visit activities.

Assessment	Information
Informed Consent	
 • Informed consent must be obtained according to the Informed Consent Process described in Appendix 2. • Counsel subjects to use adequate birth control methods required during the trial to avoid pregnancy. • Women of childbearing potential must agree to abstinence or to use at least one primary form of contraception for the duration of the study. Patients who are randomized must continue this for 60 days following the first dose (acceptable methods will be determined by the site).
Demographic variables	
 • Document the patient’s demographic variables will include items such as age, sex, ethnicity, height, weight, body mass index, and race.
Medical, surgical and smoking history	
 • Document the patient’s history of relevant current or past medical conditions, surgical history, and smoking history (current or former [yes or no]) will be obtained. Former smokers are defined as those who have stopped smoking for at least 6 months prior to Screening. • Minor surgical procedures (e.g., tonsillectomy, appendectomy) performed more than 5 years prior to Screening do not need to be recorded. • Medical condition(s) identified during Screening will be documented as medical history and not as an adverse event(s) unless the condition worsens during the trial and meets the definition of an adverse event.
Hospital admission information	
 • Document the reason for hospital admission (e.g., COVID-19 symptoms and diagnosis). Refer to Inclusion criteria in Section 5.1. • Document the most recent laboratory and imaging (radiology, hematology, chemistry, serology, urine, etc.) test results since hospital admission (Section 8.1.4).

SoC concomitant medication & supportive treatment assessment	
 • SoC concomitant medications and administered treatments must be recorded (Section 8.1.4). • Document the medications taken (for COVID-19 treatment) since admission along with the time, dose, and duration of their administration.
Brief physical examination	
 • Document the results of a physical examination performed within 4 days of randomization. • Assess the patient’s heart and lungs and document.
Safety laboratory assessments	
 • Perform Screening Hematology, Chemistry (non-fasting), Urine Analysis, Serum Pregnancy Test (as applicable) and document findings (see Appendix 3 and Exclusion criteria in Section 5.2).
Inclusion/Exclusion criteria	
 • Assess eligibility of the patient eligibility using the Inclusion (Section 5.1) and Exclusion criteria (Section 5.2). • Categorization of disease severity (Section 8.1.2).
Clinical status assessment (7-point ordinal scale)	
 • Clinical status will be assessed and recorded using the 7-point ordinal scale at the first assessment of a given study day. • See Section 8.1.1.
Vital sign assessment	
 • Vital signs will be assessed and recorded each morning at approximately the same time of a given study day. • See Section 8.1.3.

Day 1 may take place on the same day as the screening/baseline visit, if appropriate. If Day 1 activities take place on the same day as screening/baseline visit, only one 7-point ordinal scale assessment and vital signs are necessary, but they must be completed prior to dosing, if the patient is randomized to Treatment Arm 1.

Table 12. Day 1 visit activities.

Assessment	Information
Randomization	
 • Patients meeting all Inclusion criteria (Section 5.1) and none of the Exclusion criteria (Section 5.2) will be randomly assigned to one treatment arm prior to study medication treatment.
SoC concomitant medication & supportive treatment assessment	
 • SoC concomitant medications and administered treatments must be recorded (Section 8.1.4). • Document any care decisions that are made due to resource limitation.
Clinical status assessment (7-point ordinal scale)	
 • Clinical status will be assessed and recorded using the 7-point ordinal scale at the first assessment of a given study day. • See Section 8.1.1.
Vital sign assessment	
 • Vital signs will be assessed and recorded each morning at approximately the same time of a given study day. • See Section 8.1.3.

Blinded study medication dispensing	
 Study medication dispensed by study staff.
Blinded study medication training	
 pMDI Observation & Training by study staff.
Blinded study medication dosing	
 Blinded study medication administered via pMDI in the morning (4 puffs) and approximately 12 hours later in the evening (4 puffs). Document date and time taken.
Adverse Events assessments	
 The method of detecting adverse event will be performed as described in Section 8.6 and Appendix 4.

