Follow-up vital status				X	X	X		X	X	X
Re-hospitalization/Still in hospital status				X	X	X		X	X	X
Vital records search, if needed						X				X
[†]	Day 1 may take place on the same day as the screening/baseline visit, if appropriate. If Day 1 activities take place on the same day as screening/baseline visit, only 1 ordinal scale assessment and vital sign assessment are necessary, but they must be completed prior to dosing.									
[‡]	Discharge Contact: contact with the patient will take place 4 to 10 days after discharge from hospital within the 29-day treatment period. If the patient remains hospitalized after Day 29, contact with the patient will take place 4 to 10 days after receipt of last dose of study medication on Day 29.									
^{**}	Day 29 Contact (if patient discharged prior to Day 29): contact with the patient will take place 26 to 32 days after first dose of study medication. If the Discharge Contact and Day 29 Contact fall within same window, this contact will be combined as the Day 29 Contact.									
^{***}	Day 60 Follow-up: contact with the patient will take place 55 to 65 days after first dose of study medication.									
[*]	Record the physical exam documented by the treating team on the day of screening, and verify key parts (heart, lung).									
^Ω	If kidney (creatinine), liver (alanine aminotransferase or aspartate aminotransferase) and pregnancy (if applicable, via serum) were not run prior, they are required during the screening process. Refer to exclusion criteria in Section 5.2 and Appendix 3 .									
^β	Discharge safety laboratory tests may be completed at the discretion of the treating physician and, if completed, may be completed within 24 hours of the patient’s discharge from the hospital.									
[¥]	Vital signs should be recorded each morning at approximately the same time of a given study day. Variables: Respiration rate (per minute), Oxygen saturation (SpO2), Any supplemental oxygen (yes/no), Body temperature, Systolic blood pressure, Heart rate (pulse rate per minute); and Level of consciousness graded on the AVPU scale (Alert, Verbal = voice response present, Pain = pain response present, Unresponsive). Refer to Section 8.1.3 .									
¹	These assessments are not required to be completed prior to morning blinded study medication dosing.									

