4 STUDY DESIGN

4.1 Overall Design

The purpose of this study is to evaluate the effect of ensifentrine on the proportion of patients hospitalized with COVID-19 infection with recovery over 29 days.

This is a single center, randomized, double-blind, parallel group, placebo-controlled study to determine the efficacy and safety of ensifentrine 2 mg BID administered via pMDI added on to SoC treatment for COVID-19 infection compared to subjects receiving SoC plus placebo.

Patients 18 to 80 years of age must be hospitalized with a confirmed diagnosis of SARS-CoV-2 infection confirmed by PCR test and displays at least one of the following: Respiratory rate greater than 24, new cough, new atypical chest pain, new dyspnea, oxygen saturation <97% at rest, chest x-ray with new changes consistent with COVID-19 related airspace disease.

Patients meeting criteria for inclusion and none of the criteria for exclusion at randomization will be randomized to receive study medication until to hospital discharge or up to 29 days of treatment, whichever comes first. Patients will be randomized 2:1 to receive one of the following study treatments:

- Treatment Arm 1 (n=30): Blinded ensifentrine (2 mg) pMDI BID + Standard of Care treatment for COVID-19 infection
- Treatment Arm 2 (n=15): Blinded placebo pMDI BID + Standard of Care treatment for COVID-19 infection

Randomized patients will receive blinded ensifentrine or placebo twice daily, approximately 12 hours apart in the morning and evening, through 29 days or until discharge from hospital, whichever is first. Patients will self-administer 4 actuations (puffs) pMDI observed by study staff at each dosing event.

During the treatment period, patients will undergo all assessments and procedures as outlined in the SoA until hospital discharge. Patients completing treatment will complete a study contact (telephone or visit as required) within 4 to 10 days of discharge or early withdrawal. All enrolled patients will complete a telephone contact 26 to 32 days and 55-65 days following receipt of 1st dose of study medication for assessment of clinical status via the ordinal scale, need for re-hospitalization and vital status.

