6.4 Emergency Unblinding

The blind will be broken only if specific emergency treatment would require knowing the treatment status of the patient or if the protocol review committee (Section 11) recommends unblinding data for safety review reasons. If the blind needs to be broken for an individual patient, the Investigator will contact the Sponsor as soon as feasible. The Investigator may unblind the study medication immediately if he/she feels it is necessary prior to contacting the Sponsor. However, the Investigator should promptly document and explain to the Sponsor any premature unblinding. Otherwise, all blinding will be maintained until all queries are resolved and the database is locked.

The statistical vendor for this study is the site's data management group and will have access to break the blind, if necessary, but this will be kept in a secure access area.

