Appendix 5: Contraceptive Guidance and Collection of Pregnancy Information for Patients

Contraception Guidance

Male Patients

- Male patients with female partners of childbearing potential are eligible to participate if they agree to ONE of the following from the first dose up to 30 days after the last dose of study medication:
 - Are abstinent from penile-vaginal intercourse as their usual and preferred lifestyle (abstinent on a long-term and persistent basis) and agree to remain abstinent.
 - Agree to use a male condom plus partner use of a contraceptive method with a failure rate of < 1% per year when having penile-vaginal intercourse with a woman of childbearing potential who is not currently pregnant.
- In addition, male patients must refrain from donating sperm for the duration of the study and for 30 days after the last dose of study medication.
- Male patients with a pregnant or breastfeeding partner must agree to remain abstinent from penile-vaginal intercourse or use a male condom during each episode of penile penetration during the study and for 30 days after the last dose of study medication.

Female patients

Female patients of childbearing potential are eligible to participate if they are not breastfeeding and agree to either abstinence or use at least one primary form of highly effective contraception not including hormonal contraception from the time of screening through Day 60.

Pregnancy Testing:

- WOCBP should only be included after a negative highly sensitive pregnancy test.
- Additional pregnancy testing should be performed at times specified in the SoA ([Section 1.3](#)).

Pregnancy testing will be performed whenever a menstrual cycle is missed or when pregnancy is otherwise suspected.

Pregnancy testing will be performed and assayed in the central laboratory.

Collection of Pregnancy Information

Male subjects with partners who become pregnant

The Investigator will attempt to collect pregnancy information on any male patient's female partner who becomes pregnant while the male subject is in the study. This applies only to male patients who receive ensifentrine.

After obtaining the necessary signed informed consent from the pregnant female partner directly, the Investigator will record pregnancy information on the appropriate form and

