7 DEFINITIONS

7.1 General

General clinical study definitions are listed in Table 4.

Table 4. Clinical study RPL554-COV-201 general definitions.

able 4. Clinical study RPL554-COV-201 general definitions.		
Term	Definition for Study	
Baseline	The most recent pre-dose assessment prior to first dose of study medication.	
Clinical status assessment	(Protocol Section 8.1.1) Daily clinical status will be assessed using the 7-point ordinal scale adapted from the WHO R&D Blueprint expert group which measures illness severity over time (https://www.who.int/blueprint/priority-diseases/key-	
	action/COVID19 Treatment Trial Design Master Protocol synopsis Final 180 22020.pdf according to the following criteria: 1. not hospitalized, no limitations of activities 2. not hospitalized, limitation of activities, home oxygen requirement, or both 3. hospitalized, not requiring supplemental oxygen but requiring ongoing medical care* 4. hospitalized, requiring any supplemental oxygen* 5. hospitalized, requiring non-invasive ventilation or use of high-flow oxygen devices* 6. hospitalized, receiving invasive mechanical ventilation or extracorporeal membrane oxygenation (ECMO); and	
	7. death	

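### Two protocol sentences tie a procedure to the ensifentrine arm, a restriction blinded staff cannot apply: partner-pregnancy collection (Appendix 5) and, as a minor contradiction, same-day baseline timing (Section 8.2)

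*Protocol*

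**What the plan says.** Protocol 4.1 describes the design: "This is a single center, randomized, double-blind, parallel group, placebo-controlled study". It defines the arms as "Treatment Arm 1 (n=30): Blinded ensifentrine (2 mg) pMDI BID + Standard of Care treatment for COVID-19 infection" and "Treatment Arm 2 (n=15): Blinded placebo pMDI BID + Standard of Care treatment for COVID-19 infection". Patients in both arms take four puffs twice daily.

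**Partner pregnancies.** Appendix 5 asks the investigator to collect information when a male patient's partner becomes pregnant while he is in the study, and then adds: "This applies only to male patients who receive ensifentrine". With the partner's consent, the form goes to the sponsor within 24 hours of learning of the pregnancy. On unblinding, Section 6.4 says: "The blind will be broken only if specific emergency treatment would require knowing the treatment status of the patient". Its only other ground is a recommendation by the protocol review committee for safety review. Otherwise the blind is kept until database lock.

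**Baseline timing.** When screening and Day 1 fall on the same day, Section 8.2 asks for one ordinal score and one set of vital signs and says "they must be completed prior to dosing, if the patient is randomized to Treatment Arm 1". The Day 1 footnote to the Schedule of Activities (Section 1.3) covers the same situation with no arm condition: "only 1 ordinal scale assessment and vital sign assessment are necessary, but they must be completed prior to dosing". SAP 7.1, Table 4, defines baseline for every patient as "The most recent pre-dose assessment prior to first dose of study medication".

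**The concern.** Each sentence makes a procedure depend on something the design withholds from the people who carry it out.

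For partner pregnancies, what is at stake is the blind and the completeness of a safety record. An investigator who takes the sentence at its word has to learn the man's arm on a ground that Section 6.4 does not permit. One who cannot learn it has no instruction on what to do. There is a reason to want complete data: Section 2.3 reports impaired reproductive performance in male rats at the highest dose, although it found no adverse effect at 5.75 mg/kg/day, stated as 20.5 times the maximum recommended human dose by AUC.

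For baseline timing, what is at stake is consistency. Baseline feeds the change in ordinal score, the one- and two-category improvement endpoints, and the change in vital signs. A timing rule that names one arm has no place in a blinded protocol, even if other text makes it harmless in practice.

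**Working it through.** The plan states no figure on this point, so the check sets the texts side by side.

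**Partner pregnancies**

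1. The trigger in Appendix 5 is receipt of ensifentrine, which is treatment arm.
2. The investigator is blinded. The unblinded pharmacist's stated role is labelling and accountability (Section 6.3.4); no route is described for using that knowledge to filter pregnancy reports.
3. A pregnancy learned of while the man is still in the study comes before database lock, so the 24-hour report falls due while the blind is in force.
4. A partner pregnancy is neither of the two grounds in Section 6.4.
5. Possible overrides:
   - The follow-up eCRF in Section 8.1 records any pregnancy at each call without naming an arm, but does not say whether partners are included.
   - Section 8.6.5 concerns pregnancies in female patients.
   - The rest of Appendix 5 is arm-neutral: contraception rules cover all male patients, and pregnancy collection covers any female patient.

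   None of these clearly displaces the restriction.

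Result: the restriction cannot be applied while blinded. Collecting from all men can be.

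**Baseline timing, same-day screening and Day 1 only**

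| Source | Timing required | Depends on arm? |
|---|---|---|
| Section 8.2, paragraph before Table 12 | Before dosing | Yes, Arm 1 named |
| Section 1.3, Day 1 column heading | All Day 1 items before dosing | No |
| Section 1.3, Day 1 footnote | Before dosing | No |
| Section 8.2, opening paragraph | Screening/baseline and Daily eCRFs before randomization and before dose, if applicable | No |
| SAP 7.1, Table 4 | Last assessment before first dose | No |

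One sentence stands against four. The sequence of procedures then limits the consequence:

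1. Inclusion 4 requires an ordinal score of 3, 4 or 5.
2. Section 6.1 randomizes patients only after eligibility is confirmed, and randomization precedes the first dose.
3. If one score serves both visits, it is the score that established eligibility, so it is pre-dose in both arms.
4. Vital signs are listed among the screening/baseline activities in Table 11 and fall under the same eCRF timing rule.
5. The primary endpoint is recovery status at Day 29 (SAP 7.2, Table 5). Its model adjusts for treatment and COVID disease severity (SAP 9.3), not for the baseline ordinal score.

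The SAP shells head the baseline-score tables N=1 at score 3 and N=44 at score 4, and 1 + 44 = 45, the number enrolled. This shows little spread in baseline scores, but not when they were taken.

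**The case against.** The strongest reply is that these are two unrelated wording slips that a sensible site would resolve without harm. Assessing everyone before dosing satisfies Section 8.2, and the Schedule of Activities already requires it. Collecting from all men satisfies the purpose of Appendix 5. Contraception or abstinence is required, and in a 45-patient trial with dosing only in hospital the number of partner pregnancies is plausibly zero or close to it, though the documents give no figure.

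Much of this stands. A reader might infer that neither rule can be followed without breaking the blind. The documents do not support that: applying both rules to every patient keeps the blind, and only restricting them to one arm is impossible.

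A reader might also infer that up to all 15 planned placebo patients could lack a pre-dose baseline. That comes from reading one clause alone. The clause covers only the same-day case, is silent about placebo patients rather than permitting later assessment, and is contradicted by the four other sources above; under those the number is 0. Even on the literal reading, any post-dose baseline would follow placebo, so no drug effect on heart rate or any other vital sign would enter it.

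What the reply does not remove is the Appendix 5 sentence. Collecting from all men is a workable response, but it departs from an explicit limit, and the protocol should not leave that choice to the investigator under a 24-hour deadline.

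**Conclusion.** Both sentences are current protocol text and are wrong as written for a double-blind trial, because blinded staff cannot confine either procedure to the ensifentrine arm.

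Appendix 5 carries the weight. Its restriction needs knowledge of arm on neither ground that Section 6.4 allows, and no other text clearly overrides it. The size is at most one unresolved decision per partner pregnancy; the expected number is not given and is assumed to be very small. No efficacy estimate depends on it.

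Section 8.2 is a minor internal contradiction. The expected effect on baseline data is small and on the primary endpoint nil. This rests on the site following the eligibility sequence and the Schedule of Activities. The number of patients with same-day screening and Day 1 is not stated.

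**What to change.** In Appendix 5, make the partner-pregnancy sentence apply to male patients who receive blinded study medication. In Section 8.2, reconcile the same-day paragraph with the Day 1 footnote in Section 1.3 by deleting the condition on Treatment Arm 1.

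The cost is two wording changes in one protocol amendment, with its usual ethics review, and at most a few additional partner-consent and pregnancy forms for men on placebo. Sample size, dosing and the SAP analyses do not change.
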